8.5.3.2. Food-effect Assessment

A statistical analysis will be conducted to investigate the food-effect on the treatment by comparing AM1476 (fed) treatment to AM1476 (fasted) at the same dose level.

The hypothesis testing will be 2-sided and carried out on both 0.05 and 0.1 significance levels.

The ln-transformed⁵ AUC_{0-tlast}, AUC_{0- ∞}, and C_{max} on profile day 1 for food-effect group(s) in Part A (only for plasma AM1476) will be analysed using a mixed model.⁷ The model will include actual treatment as fixed effect and subject as a random effect.

For each PK parameter separately, the least squares mean (LSM) for each treatment, difference in LSMs between the fed and fasted treatments, and corresponding 90% and 95% CIs will be calculated; these values will then be back-transformed to give the GLSM, ratio of GLSMs, and corresponding 90% and 95% CIs.

Additionally, the pooled estimate (across treatments) of the within-subject CV will be calculated, and residual plots will be produced to assess the adequacy of the model(s) fitted.

Examples of the SAS code that will be used are as follows:

Mixed Model Analysis

```
proc mixed data = <data in>;
by parcatln parcatl pkday paramn param;
class trtan usubjid;
model lpk = trtan / cl residual ddfm = kr2;
lsmeans trtan / cl pdiff = control('1') alpha = 0.1;
lsmeans trtan / cl pdiff = control('1') alpha = 0.05;
random intercept / subject = usubjid;
ods output lsmeans = <data out>;
ods output diffs = <data out>;
ods output covparms = <data out>;
run;
```

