## 8.3. Pharmacokinetic Analyses

Non-compartmental PK analysis will be performed on individual plasma and urine concentration data, using commercial software such as Phoenix® WinNonlin®. Individual plasma and urine concentrations of AM1476 and plasma and urine PK parameters will be listed and summarised using descriptive statistics. Individual and mean AM1476 concentration-time profiles will also be presented graphically.

In Part A, where data are available, AM1476 dose proportionality will be examined across dose groups. The PK parameters,  $AUC_{0-\infty}$ ,  $AUC_{0-tlast}$ , and  $C_{max}$ , will be analysed for dose proportionality using a power model approach or analysis of variance (ANOVA) model as appropriate. Where data are available, the effect of food at 1 dose level in Part A will be investigated using ANOVA. To investigate the effect of food on the PK of AM1476, the log-transformed AUC0-∞, AUC0-tlast, and Cmax values for AM1476 administered with and without food will be analysed using a linear mixed-effects model with treatment as fixed effect and subject as a random effect. Point estimates and 90% confidence intervals (CIs) for differences between the treatments (fed versus fasted) on the log scale will be exponentiated to obtain estimates for the ratios of geometric means and respective 90% CIs on the original scale.

In Part B,  $AUC_{0-\tau}$  and  $C_{max}$  on Day 10 will be analysed for dose proportionality using a power model approach or ANOVA model as appropriate.

Additional details will be presented in the Statistical Analysis Plan (SAP).

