8. STATISTICAL METHODOLOGY

8.1. General

Listings will be provided for all data captured in the database, with the exception of medical history. Listings will include all subjects assigned to the all subjects population and include data up to the point of study completion or discontinuation. Subjects are generally considered to have completed the study if they complete the scheduled follow-up visit (rather than early termination visit). Any subject who discontinues the study will be identified accordingly in the listings. Summaries and statistical analyses will include the subjects assigned to the relevant population based on data type.

Analysis Data Model (ADaM) datasets will be prepared using Clinical Data Interchange Standards Consortium (CDISC) ADaM Version 2.1 (or higher if a new version is issued during the study) and CDISC ADaM Implementation Guide Version 1.1 (or higher if a new version is issued during the study). Pinnacle 21 Community Validator Version 3.0.2 (or higher if a new version is issued during the study) will be utilised to ensure compliance with CDISC standards.

For all statistical analyses, the hypothesis testing will be 2-sided and carried out on 0.05 significance level, unless specifically stated otherwise.

Caution should be used when interpreting results from the statistical analyses conducted in this study because the sample size is not based on power calculations.

Where reference is made to 'valid' data, this refers to non-missing data which meet the predetermined criteria (eg, are not flagged for exclusion).

Where reference is made to 'all calculations', this includes, but is not limited to, summary statistics, statistical analyses, baseline derivation, and changes from baseline.

All figures will be produced on linear-linear or discrete-linear scales, as applicable, unless specifically stated otherwise.

8.1.1. Handling of Data Quality Issues Due to Coronavirus Disease 2019 and Related Restrictions

Due to COVID-19 and related restrictions, there is a high risk for impact to data integrity, with the recognised potential for:

- Missed visits, caused by, for example:
 - Subject unable to travel to site due to restrictions, the need to quarantine, or COVID-19 infection
 - o Subject unwilling to go to site due to fear of COVID-19 infection
 - Site postponing subject's visit due to investigator not being available (eg, if they have been dispatched to hospital handling COVID-19 infections)

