8.5.3. Pharmacokinetic Statistical Methodology

8.5.3.1. Dose Proportionality Assessment

A statistical analysis will be conducted to investigate the dose proportionality of AUC_{0-tlast}, AUC_{0- ∞}, and C_{max} on profile day 1 for Part A and AUC_{0- τ} and C_{max} on profile day 10 for Part B (only for plasma AM1476).

The PK parameters will be analysed using a power model⁴ that will have the following form:

parameter = *intercept* × *dose*^{*slope*} × *random error*

Using the natural log (ln) transformation,⁵ a power model can be expressed as a linear regression equation:

 $ln(parameter) = intercept + slope \times ln(dose) + random error$

For dose proportionality, the slope of the regression line is equal to 1; for dose independence, it is equal to 0.

For each PK parameter separately, a pooled estimate (across all doses) of slope, corresponding 95% confidence interval (CI), and between-subject CV will be calculated. Figures (on the logarithmic-logarithmic scale) containing individual values, power model line (95% CI), and dose proportionality line (defined as the power model line with slope of 1) will be created for each PK parameter. Additionally, figures (on the logarithmic-linear scale) containing individual values and geometric means will be created for each corresponding PK parameter normalised by dose administered.

The lack of fit test will be conducted for the statistical assessment of linearity assumption, and thus appropriateness of a power model. The lack of fit model will be the same as the power model fitted, but with dose included as additional fixed effect. The statistical assessment will rule the linearity assumption acceptable if the diagnostic plots appear reasonable and the lack of fit 2-sided p-value >0.05 (dose effect is not significant at the 0.05 level of significance). The assessment of linearity assumption may also occur via visual examination of the figures by the pharmacokineticist. This assessment may override the statistical assessment; where this occurs, it will be detailed in the CSR.

It will be concluded that PK parameter is dose proportional for the dose range studied if the assumption of linearity is ruled acceptable and the 95% CI for the slope spans 1.

If the assumption of linearity is ruled unacceptable for any PK parameter, its corresponding PK parameter normalised by dose administered will be ln-transformed and analysed using an analysis of variance (ANOVA) model.⁶ The model will include dose as a factor.

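### Does the SAP need to say which of its two food-effect significance levels, 0.05 or 0.1, governs?

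*SAP*

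**What the plan says.** Protocol section 8.3 plans the food-effect analysis as estimation. It uses a linear mixed-effects model on the log scale, with treatment fixed and subject random, and then "Point estimates and 90% confidence intervals (CIs) for differences between the treatments (fed versus fasted) on the log scale", which are exponentiated to ratios. It names no test and no significance level.

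SAP section 8.5.3.2 keeps the model, the ratio and the 90% interval. It adds tests: "The hypothesis testing will be 2-sided and carried out on both 0.05 and 0.1 significance levels". It also adds a 95% interval: "these values will then be back-transformed to give the GLSM, ratio of GLSMs, and corresponding 90% and 95% CIs". The example code has two least-squares-means statements that differ only in alpha, 0.1 and 0.05.

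The SAP default in section 8.1 reads "For all statistical analyses, the hypothesis testing will be 2-sided and carried out on 0.05 significance level, unless specifically stated otherwise". The same section warns: "Caution should be used when interpreting results from the statistical analyses conducted in this study", because the sample size does not come from a power calculation.

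For dose proportionality, section 8.5.3.1 does give a conclusion rule: "It will be concluded that PK parameter is dose proportional for the dose range studied if the assumption of linearity is ruled acceptable". Its second condition is that the slope's 95% interval covers 1. Section 8.5.3.2 has no counterpart.

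**The concern.** Two significance levels with no ranking look like an invitation to choose after seeing the result. The 0.05 default does not settle it, since it gives way wherever a section states otherwise, and 8.5.3.2 does. The protocol's 90% interval does not plainly settle it either, since SAP section 1 says the SAP supersedes the protocol's statistical considerations.

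If p fell between 0.05 and 0.10, the 90% interval would exclude a ratio of 1 and the 95% interval would include it. A report could then stress a food effect or a non-significant one, and either statement would comply with the SAP. The food effect is a named secondary objective, and the protocol's study rationale wants it characterised before patient studies. At stake is the wording of the conclusion, for three parameters: AUC to the last quantifiable concentration, AUC to infinity, and Cmax.

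**Working it through.** The documents give no power, sample-size or error-rate figure for the food effect, so there is nothing of the plan's own to reproduce. Two checks remain: how often the levels disagree, and what depends on the disagreement.

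**Inputs**
- Active subjects in the food-effect group: 6 (Protocol section 3.1.1).
- Model: treatment fixed, subject random (SAP section 8.5.3.2). With complete pairs and a positive between-subject variance estimate, this is a paired t-test on log values with 6 − 1 = 5 df.
- Within-subject CV: not given. Assumed range 15% to 40%.

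**Formulas**
- σ_w = √ln(1 + CV²); SE of the log ratio = σ_w × √(2/6).
- Critical values on 5 df: 2.015 (two-sided 0.10) and 2.571 (two-sided 0.05). These are also the multipliers for the 90% and 95% intervals, so each level is the same statement as its interval.
- The levels disagree when 2.015 < |t| < 2.571, that is, for observed ratios from exp(2.015 × SE) to exp(2.571 × SE), or their reciprocals.
- Chance of disagreement = power at 0.10 − power at 0.05 (noncentral t).

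**No food effect.** 0.10 − 0.05 = 5% per parameter, whatever the CV. For at least one of three parameters, if they were independent: 1 − 0.95³ = 14.3%. The two AUCs and Cmax are correlated, so this is an upper-end illustration.

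**True food effect**

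| Assumed CV | SE | Observed ratio where levels disagree | Chance, true ratio 1.25 | Chance, true ratio 1.5 |
|---|---|---|---|---|
| 15% | 0.0861 | 1.19–1.25 | 17% | 3% |
| 20% | 0.1143 | 1.26–1.34 | 16% | 11% |
| 25% | 0.1422 | 1.33–1.44 | 14% | 16% |
| 30% | 0.1695 | 1.41–1.55 | 12% | 17% |
| 40% | 0.2224 | 1.57–1.77 | 10% | 16% |

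**Worked case, CV 20%.** Take an observed ratio of 1.30. Then t = ln(1.30)/0.1143 = 2.29 and p = 0.070. The 90% interval is 1.03 to 1.64 and the 95% interval is 0.97 to 1.74.

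**What the output would show.** In the SAP code, alpha sets only the confidence level. The difference, its standard error and its p-value are the same from both statements. The report for the worked case would show 1.30, p = 0.070 and both intervals.

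**What depends on it.**
- Section 8.5.3.2 attaches no conclusion to the test.
- The dietary state in Part B follows a review of the fed/fasted PK data (Protocol sections 3.1.2 and 5.2), not a significance test.
- Sample size has no formal basis (Protocol section 8.1, SAP section 5), and no error rate is claimed for this comparison.

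**The case for a change.** The best case for a change is that the SAP wrote a conclusion rule for the neighbouring secondary PK analysis and left this one open, although one paragraph would close it. The disagreement falls at moderate ratios, where a reader most wants a single prespecified reading. With 6 pairs a non-significant result also says little: power at 0.05 for a true ratio of 1.25 runs from 55% at a CV of 15% down to 13% at 40%. The SAP does not warn specifically against reading non-significance as absence of an effect.

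Part of this stands. No text ranks the two levels or the two intervals, and the arithmetic above is right. But nothing in the plan draws a no-effect conclusion from a non-significant test, and section 8.1 already asks for caution because the study was not sized by power. That a p-value of 0.07 lies between 0.05 and 0.10 is true of any two levels, and anyone reading the table will see it. Because both intervals are prespecified, selective wording would be visible beside the full result.

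There is also a partial anchor. The protocol names only the 90% interval, and SAP section 10 declares no significant change from the protocol's analyses. The natural reading is that the 90% interval remains the planned result and the 95% interval is an addition at the SAP's usual level. The superseding clause in SAP section 1 keeps that reading from being conclusive.

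**Conclusion.** No change follows. The SAP omits a ranking that a careful author would probably have written, but carrying it out as it stands gives a correct ratio, one p-value and two correct nested intervals for each parameter. The levels disagree in 5% of trials per parameter under no food effect, and in roughly 3% to 17% at true ratios of 1.25 and 1.5. These figures assume 6 complete pairs; the second range also assumes a within-subject CV of 15% to 40%. Disagreement affects only how a sentence in the report is phrased. No estimate is wrong or lost, and no stated decision turns on it. Analysts can reasonably lead with the protocol's ratio and 90% interval and treat the 95% interval and the test as supplementary, without an amendment.

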8.6. Safety and Tolerability Assessments

8.6.1. Adverse Events

All AEs will be coded using the Medical Dictionary for Regulatory Activities (MedDRA) Version 23.1 (or higher if a new version is issued during the study; see the DMP for more details).

A treatment-emergent adverse event (TEAE) will be defined as an AE that starts during or after the first dose, or starts prior to the first dose and increases in severity after the first dose.

A treatment-related TEAE will be defined as a TEAE with a relationship of possibly related or related to the study treatment, as determined by the investigator.

All AEs will be listed. In addition to the data recorded in the database, the listings will include derived onset time and duration. Onset time will be calculated from the time of the last associated dose for TEAEs only. Where the last associated dose is referring to the last dose received prior to the start of a TEAE.

The frequency of subjects with TEAEs and the number of TEAEs will be summarised for the following categories:

- TEAEs (overall, serious, leading to discontinuation, and leading to death) by treatment
- TEAEs by severity and treatment
- Treatment-related TEAEs (overall, serious, leading to discontinuation, and leading to death) by treatment
- Treatment-related TEAEs by severity and treatment

The frequency of subjects will be summarised separately for TEAEs and treatment-related TEAEs by the following:

- System organ class, preferred term, and treatment
- Preferred term and treatment

For the AE data the following rules will apply:

- For the derivation of relationship (applicable to AEs captured on the 'change in the severity' eCRF form only): The relationship to study treatment is not captured on the AE change in severity eCRF form because it is always assumed to be the same as the relationship captured on the first eCRF form completed for this AE (initial severity). Therefore, for these cases the missing relationship will be set to that captured on the first form completed for this AE.
- For the derivation of treatment-emergent status (applicable to all AEs): If the start date/time of an AE is incomplete or missing, an AE will be assumed to not be a TEAE, unless the incomplete start date/time or the end date/time indicates an AE started after the first dose.
- For the derivation of treatment-related status (applicable to TEAEs only): If the study treatment relationship for a TEAE is missing, a TEAE will be assumed to not be a treatment-related TEAE.
- For the derivation of onset time (applicable to TEAEs only): If the start date/time of a TEAE is missing, onset time will not be calculated. If the start date/time of a TEAE is incomplete, where possible, the minimum possible onset time will be calculated and presented in '≥DD:HH:MM' format (eg, if the date/time of the last associated dose is 01MAY2019/08:00 and recorded start date/time of a TEAE is 03MAY2019, then the minimum possible onset time will be calculated by assuming a TEAE started at the first hour and minute of 03MAY2019 [03MAY2019/00:00], thus will be presented as onset time ≥01:16:00 in the listing). If the start date of a TEAE is the same as the date of the last associated dose but the start time of a TEAE is missing, an onset time will be presented as '≥00:00:01'. Any clock changes will be accounted for in the derivation.
- For the derivation of duration (applicable to all AEs): If the end date/time of an AE is missing, duration will not be calculated. If the start or end date/time of an AE is incomplete, where possible, the maximum possible duration will be calculated and presented in '≤DD:HH:MM' format (eg, if the start of an AE date/time is 01MAY2019/08:00 and its recorded end date/time is 03MAY2019, then the maximum possible duration will be calculated by assuming an AE ended at the last hour and minute of 03MAY2019 [03MAY2019/23:59], thus will be presented as duration ≤02:15:59 in the listing). Any clock changes will be accounted for in the derivation.
- For the calculation of TEAE summary statistics: If the severity of a TEAE is missing, that TEAE will be counted under the 'missing' category.

• For the calculation of TEAE summary statistics: If a subject experienced multiple TEAEs with the same preferred term for the same treatment, this will be counted as 1 TEAE for that treatment under the maximum severity recorded.

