#### 3.7. Dose Escalation Stopping Criteria

The study will be halted if 1 or more subjects experience a serious adverse event (SAE) that is considered to be related to IMP or 2 or more subjects in the same group experience severe AEs that are considered to be related to IMP. If, following an internal safety review, the Sponsor deems it appropriate to restart the study, this can be done following approval of a substantial protocol amendment.

Dosing of subjects, including any ongoing multiple dose groups, will be stopped immediately if any of the dose escalation stopping criteria (Section 3.7) are met.

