## **Relationship to Study Treatment**

The Investigator (or designee) will make a determination of the relationship of the AE to the study treatment using a 4-category system according to the following guidelines:

- Not Related: The AE is definitely caused by the subject's clinical state or the study procedure/conditions.
- Unlikely Related: The temporal association between the AE and the drug is such that the drug is not likely to have any reasonable association with the AE.
- **Possibly Related:** The AE follows a reasonable temporal sequence from the time of drug administration but could have been produced by the subject's clinical state or the study procedures/conditions.
- **Related:** The AE follows a reasonable temporal sequence from administration of the drug, abates upon discontinuation of the drug, follows a known or hypothesised cause-effect relationship, and (if appropriate) reappears when the drug is reintroduced.

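### SAP 8.6.1 can drop an untimed first-dosing-day AE from every AE summary table, against its own same-day onset rule, and counts a missing relationship as not treatment-related

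*SAP*

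**What the plan says.** SAP 8.6.1 (Adverse Events) sets three rules that matter here.

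- **Treatment emergence.** A TEAE begins during or after the first dose, "or starts prior to the first dose and increases in severity after the first dose". When the start is incomplete or absent, the AE is "assumed to not be a TEAE, unless the incomplete start date/time or the end date/time indicates an AE started after the first dose".
- **Missing relationship.** "If the study treatment relationship for a TEAE is missing, a TEAE will be assumed to not be a treatment-related TEAE".
- **Change in severity.** The eCRF form for a change in severity has no relationship field, so "the missing relationship will be set to that captured on the first form completed for this AE".

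Three other provisions bear on these. SAP 8.6.1 displays an onset of ≥00:00:01 for a TEAE that shares its date with the last associated dose but has no start time. It places a TEAE without a severity grade in a missing category. SAP 8.1.2 sets the general convention for categorical data: no imputation unless the SAP says otherwise, and a missing category where information is absent.

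The AE summaries listed in SAP 8.6.1 are all of TEAEs or treatment-related TEAEs. Every AE is listed, but "Onset time will be calculated from the time of the last associated dose for TEAEs only".

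**The concern.** AE incidence and severity is the first-listed primary endpoint (Protocol 2.2.1, SAP 3.1). SAP 8.6.6 plans no inferential safety analysis, so the TEAE tables are the main AE summary of a first-in-human study. In a single-dose group, the first dosing day is when an acute drug effect is most likely to be reported. A rule that sets an untimed AE from that day aside as non-emergent works against the purpose of the table.

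The text also contains a conflict and a gap. One sentence expects untimed dosing-day AEs to be TEAEs while another appears to exclude them, and two programmers could flag the same AE differently. The date rule admits only a post-dose start as an exception, so it ignores the worsening limb of the SAP's own TEAE definition.

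Missing relationship is set to the less cautious value, while missing severity in the same section is left visible.

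**Working it through.** **1. Apply the date rule to test cases.** Assume, for illustration, a first dose at 08:00 on Day 1. The literal reading requires the recorded data to show a start after the dose. The lenient reading lets a recorded end after the dose suffice, unless the partial start already rules out a post-dose onset.

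| Recorded start | Recorded end | Literal | Lenient | Rule in the fix |
|---|---|---|---|---|
| Day 1, no time | none (ongoing) | not TEAE | not TEAE | TEAE |
| Day 1, no time | Day 2 | not TEAE | TEAE | TEAE |
| Day 2, no time | any | TEAE | TEAE | TEAE |
| Day -1, no time, no worsening | any | not TEAE | not TEAE | not TEAE |
| Day -1, no time, worse on Day 2 | any | not TEAE | not TEAE | TEAE |
| missing | before dose | not TEAE | not TEAE | not TEAE |
| missing | Day 2 | not TEAE | TEAE | TEAE |

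The fifth row is a TEAE by the SAP's definition but not by its date rule.

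**2. Set the end-date exception against logic.** An end before the dose proves a pre-dose start. An end after the dose is compatible with a start on either side. Taken literally, the end date can therefore never supply the proof that the exception asks for.

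**3. Set the date rule against the ≥00:00:01 rule.** In Groups A1, A2 and A4 to A6 the only dose is the first dose. On the literal reading, an AE with that date and no time is never a TEAE, and the onset rule covers TEAEs only, so it has nothing to act on. It could operate only for later doses: Group A3 Period 2, any added food-effect group in its second period, and Part B after Day 1.

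**4. Compare the handling of missing values within 8.6.1.** Missing severity is kept and shown as missing. Missing relationship is imputed as not related. SAP 8.1.2 allows stated exceptions, so this is not a contradiction. It is a departure from the convention with no reason given.

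**5. Check the relationship carry-forward.** In Protocol Appendix 1, Possibly Related requires that "The AE follows a reasonable temporal sequence from the time of drug administration", and Related that "The AE follows a reasonable temporal sequence from administration of the drug, abates upon discontinuation of the drug". An assessment made before any dose can meet neither. If the first form was completed before dosing and is not updated, a pre-dose AE that worsens on treatment is a TEAE that cannot enter the treatment-related tables. The carry-forward also works the other way: a mild post-dose AE rated related that later worsens for another reason is counted as related at its maximum severity.

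**6. Size.** The plan gives no figure to reproduce. For one subject whose only TEAE is moved, the shift is 100/n, with n from the planned design:

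- one active group, n = 6: 100/6 = 16.7 points
- Part A pooled placebo, n = 6 × 2 = 12: 100/12 = 8.3 points
- Part B pooled placebo, n = 3 × 2 = 6: 100/6 = 16.7 points
- all Part A active subjects, n = 6 × 6 = 36: 100/36 = 2.8 points

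Exact (Clopper-Pearson) 95% limits are 0.4% to 64.1% for 1/6 and 0% to 45.9% for 0/6.

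**The case against.** The strongest reply is that the literal reading is not the intended one. It leaves the end-date exception without effect and the ≥00:00:01 rule idle in most of Part A, and a reader normally prefers an interpretation that gives every sentence work to do. On the lenient reading, an untimed Day 1 AE with a recorded end after dosing is kept. This stands as far as it goes, and it is why the point is a conflict to reconcile rather than a settled rule that always excludes such AEs. It does not rescue an untimed Day 1 AE that is ongoing or has no usable end, and it does not restore the worsening limb.

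The second reply is that the cases will be rare. Protocol 7.2.1 requires onset time and the investigator's causality opinion in the source data, and resident subjects are questioned at least daily. Protocol Appendix 5 adds source verification and query resolution. That is fair. SAP 8.1.1 does, however, foresee incomplete entry and unanswered queries because of COVID-19 restrictions.

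A reader might infer that all these defaults can only lower counts. The documents do not support that for the carry-forward, which can also raise the treatment-related severity counts. A reader might also infer that causality at worsening is never collected. The SAP says only that one form does not capture it; source data may hold it, and the documents do not show whether the first form can be updated.

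Finally, the one-subject shift would be the same whatever moved the subject. It shows how sensitive small groups are and does not estimate a bias.

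**Conclusion.** The point holds as a minor defect in the SAP. The emergence default, read literally, can remove an untimed first-dosing-day AE from every AE summary table. It conflicts with the same-day onset rule, has an ambiguous end-date exception and omits worsening. The missing-relationship rule takes a TEAE out of the treatment-related tables with no visible trace there. The carry-forward problem is conditional on the first form not being revised after dosing.

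The number of affected events cannot be computed from the documents and should be small. If no start or relationship is missing and no pre-dose AE worsens, nothing changes. Otherwise one subject is worth 16.7 points in a 6-subject active group. The rules apply to active and placebo alike.

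A reader might infer that dose decisions are at risk. The documents do not support this: the halting rule in Protocol 3.7 turns on whether "1 or more subjects experience a serious adverse event (SAE) that is considered to be related to IMP", or on related severe AEs in the same group, as judged during the study and not on these derivations. No AE is lost from the listings, although one set to non-TEAE loses its derived onset time. The exposure is confined to the reported tables.

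**What to change.** Amend SAP 8.6.1 before any unblinding for analysis.

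- **(a) Emergence.** Treat an AE with an incomplete or missing start as a TEAE unless the partial start or the end date/time shows that it began before the first dose and it did not increase in severity afterwards. This also reconciles the default with the ≥00:00:01 rule. State which column, fasted or fed, receives a wholly undated AE in Group A3.
- **(b) Missing relationship.** Do not count it as not related. Show it in a missing row of the treatment-related tables, in line with SAP 8.1.2, or count it as related. Flag it in the listing either way.
- **(c) Worsened pre-dose AEs, if the first form is not updated after dosing.** Seek the investigator's relationship at worsening by query. If none is obtained, flag the AE in the listing as having only a pre-dose assessment, and leave the investigator's recorded value unchanged.

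The cost is a few sentences of SAP text and some queries under (c), because the change-in-severity form has no relationship field. No extra subjects or visits are needed. The downside is that a few events may be over-counted as emergent or related, including undated AEs from a screening period of up to 28 days (35 days in Group A1).
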